**Treatment Period 1 (subjects who participate in Treatment Period 2):**

Week 13 Day 85/91 Visit date and time – 1 – date and time of first administration of study treatment + 1.

**Treatment Period 1 (subjects who do NOT participate in Treatment Period 2):**

Study Completion Visit date and time – date and time of first administration of study treatment + 1.

**Treatment Period 2 (subjects without dose change):**

Study Completion Visit date and time – Week 13 Day 85/91 Visit date and time + 1.

**Treatment Period 2 (subjects with dose change):**

Portion before dose change:

Date and time of dose change – Week 13 Day 85/91 Visit date and time + 1.

Portion after dose change:

Study Completion Visit date and time – Date and time of dose change.

**Treatment Period 1 and 2 (subjects without dose change):**

Study Completion Visit date and time – date and time of first administration of study treatment + 1.

**Treatment Period 1 and 2 (subjects with dose change):**

Portion before dose change:

Date and time of dose change – date and time of first administration of study treatment + 1.

Portion after dose change:

Data will not be included in the summary tables.

**Safety Analysis AEs:** The duration in days of the evaluation periods will be:

**Treatment Period 1 (subjects who receive an IV loading dose of investigational product and who participate in Treatment Period 2):**

Week 13 Day 91 Visit date and time – 1 – Week 1 Day 6 Visit of Treatment Period 1 date and time (the date / time of the first SC administration of investigational product in Treatment Period 1) + 1.

**Treatment Period 1 (subjects who receive an IV loading dose of investigational product and who do NOT participate in Treatment Period 2):**

Follow-up or Study Completion Visit date and time (whichever occurs later) – Week 1 Day 6 Visit of Treatment Period 1 date and time (the date / time of the first SC administration of investigational product in Treatment Period 1) + 1.

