2.2.2 Secondary Endpoints

Table 2 Secondary Endpoints

Secondary Objective	Secondary Endpoints	Summary Measure(s)
1	Responder subjects.	The number and percentage of subjects with C1-INH HAE who respond to treatment with CSL312 or placebo during Treatment Period 1, where “response” is defined as a $\geq 50\%$ relative reduction in the time-normalized number of HAE attacks (per month) compared to each subject’s time-normalized

Secondary Objective	Secondary Endpoints	Summary Measure(s)
		number of HAE attacks (per month) during the Run-in Period.
1	HAE attack-free subjects.	The number and percentage of subjects with C1-INH HAE who do not experience an HAE attack on treatment with CSL312 or placebo during Treatment Period 1.
1	HAE attacks.	The number, time-normalized number (per month), and percentage of mild, moderate, or severe HAE attacks in subjects with C1-INH HAE on treatment with CSL312 or placebo during Treatment Period 1.
1	HAE attacks treated with on-demand HAE medication.	The number, time-normalized number (per month), and percentage of mild, moderate, or severe HAE attacks in subjects with C1-INH HAE treated with on-demand HAE medication on treatment with CSL312 or placebo during Treatment Period 1.
2	CSL312 PK in plasma: 
 • Maximum concentration (C_{max}). • Area under the concentration-time curve in 1 dosing interval ($AUC_{0-\tau}$). • Time of maximum concentration (T_{max}). • Terminal elimination half-life ($T_{1/2}$). • Total systemic clearance (CL_{tot}). 	CSL312 concentration in plasma in subjects with C1-INH HAE during treatment with CSL312 or placebo at specified time points during Treatment Period 1.

Secondary Objective	Secondary Endpoints	Summary Measure(s)
	
Volume of distribution during the elimination phase (V_z).	
3	Subjects experiencing: 
AEs.SAEs.AEs of special interest (ie, anaphylaxis, TEEs, and bleeding events).ISRs.Inhibitory antibodies to CSL312.Clinically significant abnormalities in laboratory assessment that are reported as AEs.	The number and percentage of subjects with C1-INH HAE experiencing the specified safety events on treatment with CSL312 or placebo during Treatment Period 1.

Abbreviations: AEs = adverse events; HAE = hereditary angioedema; C1-INH HAE = Hereditary angioedema with C1-esterase inhibitor deficiency; ISRs = injection site reactions; SAEs = serious adverse events; TEEs = thromboembolic events.

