8.5.2.10 Treatment Period 1 Follow-up Visit

Subjects who do not participate in Treatment Period 2 will attend a Follow-up Visit at Week 26 (Day 186 ± 3 days).

The following procedures will be conducted at the Week 26 (Day 186) Treatment Period 1 Follow-up Visit:

- Collection of blood to assess PK / (b) (4)
- Review eDiary data, including investigator assessment of HAE symptoms and documentation of HAE attacks.
- Concomitant medications and therapies.
- Adverse events.
- Close eDiary access (for subjects who will not participate in Treatment Period 2).

Note 1: If a subject participates in Treatment Period 2, then the subject will not attend the Treatment Period 1 Follow-up Visit.

Note 2: The Treatment Period 1 Follow-up Visit may be waived in place of a telephone contact. If Treatment Period 1 Follow-up is not conducted as a visit, then the blood draw for assessment of PK / (b) (4) is not required.

8.5.3 Treatment Period 1 for C1-INH HAE Subjects Receiving Investigational Product Every 2 Weeks

All subjects should remain at the study site for at least 30 minutes after the administration of investigational product when administered at the study site.

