8.5.3.10 Treatment Period 1 Follow-up Visit

Subjects who do not participate in Treatment Period 2 will attend a Follow-up Visit at Week 25 (Day 180 ± 3 days).

The following procedures will be conducted at the Week 25 (Day 180) Treatment Period 1 Follow-up Visit:

- Collection of blood to assess PK / [REDACTED]
- Review eDiary data, including investigator assessment of HAE symptoms and documentation of HAE attacks.
- Concomitant medications and therapies.
- Adverse events.

- Close eDiary access (for subjects who will not participate in Treatment Period 2).

Note 1: If a subject participates in Treatment Period 2, then the subject will not attend the Treatment Period 1 Follow-up Visit.

Note 2: The Treatment Period 1 Follow-up Visit may be waived in place of a telephone contact. If Treatment Period 1 Follow-up is not conducted as a visit, then the blood draw for assessment of PK / [REDACTED] is not required.

8.5.4 Treatment Period 2

All subjects should remain at the study site for at least 30 minutes after the administration of investigational product when administered at study visits.

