**Treatment Period 1 (CCI [REDACTED]):**

Week 13 Day 85 Visit date and time – 1 – Week 1 Day 1 Visit of Treatment Period 1 date and time (the date / time of first SC administration of investigational product in Treatment Period 1) + 1.

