### 11.3 Adverse Events

TEAEs are AEs which start on or after the date and time of the first administration of study treatment. TEAEs with a start date and time on or after the administration of the IV loading dose and before the first administration of SC investigational product will be analyzed separately from TEAEs with start date and time on or after the first administration of SC investigational product.

AEs with completely or partially missing date or time will be considered treatment-emergent following the worst-case principle, unless the partial date clearly indicates that the AE started before the first administration of study treatment. AEs with completely missing start dates will be considered treatment-emergent. If only the day is missing, and the start month and year of the AE is before the start month and year of the first administration of study treatment, the AE will be considered non-treatment-emergent. If day and month are missing and the start year of the AE is before the year of the first administration of study treatment, the AE will be considered non-treatment-emergent.

AEs will be coded by MedDRA. There will be periodic updates of the MedDRA version. The latest licensed version will be used, and version updates will be implemented upon availability. AEs will be primarily classified by MedDRA PT. Analyses will be performed by SOC and PT. Aggregated incidences at SOC level and Any TEAE will also be provided.

TEAEs occurring until the Follow-up Visit will be summarized. All AEs regardless of when they were reported will be listed.

Summaries of TEAEs will count the number of subjects, that is, subjects with multiple occurrences of the same TEAE will be counted once in the total of those experiencing this PT. Similarly, a subject with 1 or more PT in a SOC will be counted once in the total of those experiencing PTs in that SOC. Percentages for subject incidence rates will be based on the Safety population.

CCI

CCI [REDACTED] The MedDRA SOCs and PTs will be presented in descending frequency of the overall CSL312 category. Within the same frequency, SOCs and PTs will be ordered alphabetically.

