The tables referring to TEAEs on or after first SC injection will comprise two parts: one – indicated in the numbering by x.1 – containing the number of subjects, percentage of subjects, and number of events, and the other – indicated in the numbering by x.2 – containing the event rates per administration and per subject year. The tables referring to TEAEs on or after the IV loading dose and before the first SC injection will comprise only the first part (number and percentage of subjects and number of events) as described above and no rates.

AE rates per SC injection for each safety evaluation period will be calculated as follows:

- AE Rate per SC Injection =  $\frac{\text{Number of events for a particular PT}}{\text{Number of SC injections}}$

where number of SC injections will be the sum of the SC injections that subjects received during the respective safety evaluation period.

- AE Rate per Subject SC Year =  $\frac{\text{Number of events for a particular PT}}{\text{Subject SC years}}$

where subject SC years will be the sum of the time in years that subjects were exposed to study treatment administered by SC injections during the respective safety evaluation period (sum of the duration after SC injections of the respective safety evaluation period in years).

The safety evaluation periods (Treatment Period 1, Treatment Period 2, and overall) are defined for the Safety analysis in Section 8.2.8.

For TEAEs which started on or after the IV loading dose but before the first SC dose, a summary table as described below will be provided and a table of TEAEs by SOC and PT as described below.

An overview summary of TEAEs will be provided as specified in Section 7 for:

- Any TEAE;
- Any SAEs;
- Any SAEs caused by COVID-19;
- Any deaths;

- Any deaths caused by COVID-19;
- TEAEs occurring within 24 hours of investigational product administration;
- Relates TEAEs;
- TEAEs leading to study discontinuation;
- TEAEs leading to study discontinuation caused by COVID-19;
- TEAEs in each intensity category;
- TEAEs in each outcome category;
- TEAEs not resolved or resolved with sequelae caused by COVID-19.

The following summary tables will be provided as specified in Section 7 for:

- TEAEs by SOC and PT;
- TEAEs by intensity, SOC, and PT;
- Related TEAEs by SOC and PT;
- TEAEs leading to study discontinuation by SOC and PT;
- Non-serious TEAEs by SOC and PT;
- Laboratory Findings reported as AEs.

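### Treatment Period 1 adverse-event windows run to Week 13 for subjects who enter Treatment Period 2 but to the Follow-up Visit for those who do not, so the percentages and per-injection rates include post-period events for non-continuers only

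*SAP*

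**What the plan says.** Protocol 2.2.2, Table 2, defines the secondary safety endpoint as the number and percentage of C1-INH HAE subjects "experiencing the specified safety events on treatment with CSL312 or placebo during Treatment Period 1".

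SAP 8.2.8, under Safety Analysis AEs, gives two Treatment Period 1 windows for subjects who receive an IV loading dose:

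- Subjects who enter Treatment Period 2: "Week 13 Day 91 Visit date and time – 1 – Week 1 Day 6 Visit of Treatment Period 1 date and time", plus 1.
- Subjects who do not: "Follow-up or Study Completion Visit date and time (whichever occurs later) – Week 1 Day 6 Visit" of Treatment Period 1, plus 1.

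Two further definitions start at Week 1 Day 1. Their labels are redacted, but the visit days identify the q2wk arm, and they split the same way: one is "Week 13 Day 85 Visit date and time – 1 – Week 1 Day 1 Visit of Treatment Period 1 date and time", plus 1, and the other runs to the later of Follow-up or Study Completion.

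SAP 11 applies the 8.2.8 periods to the safety analysis. SAP 11.3 adds that "TEAEs occurring until the Follow-up Visit will be summarized". It also gives a rate per SC injection, "where number of SC injections will be the sum of the SC injections that subjects received during the respective safety evaluation period", and a rate per subject-year over the safety evaluation period. The reporting columns in SAP 7 are Treatment Period 1, Treatment Period 2 and the two combined. None is for follow-up.

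**The concern.** A non-continuer's follow-up events have only the Treatment Period 1 column to enter, whereas a continuer's own follow-up is assigned to Treatment Period 2. The Treatment Period 1 percentages therefore mix subjects watched for about 12 weeks with subjects watched for up to about 26. They also count events that the protocol's endpoint definition places outside the period.

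The SAP does not do this elsewhere. For the same non-continuers, its exposure window stops at the Study Completion Visit, and its efficacy analysis excludes attacks that start between the last treatment-period visit and Follow-up.

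Continuation is decided after randomization and may be related to outcome. SAP 7 lists a sequence with no Treatment Period 2 treatment for every arm, SAP 4.5 allows for one dropout per arm, and SAP 10.1.2 plans to look for dropouts caused by many attacks. If more subjects leave one arm than another, the percentages in that arm rise from longer observation alone. With 8 subjects per arm, a few such subjects can move a safety percentage.

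**Working it through.** **Inputs.** From the protocol: Week 13 is Day 91 (q4wk) or Day 85 (q2wk); Treatment Period 1 Follow-up is Day 186 (8.5.2.10) or Day 180 (8.5.3.10); q4wk SC doses fall on Days 6, 35 and 63; early stoppers also attend Follow-up ~14 weeks after their discontinuation assessments (8.5.5); half-life is ~19 days (1.2.3.1). The window formulas come from SAP 8.2.8. The documents give no adverse-event rate, so the rates below are assumptions.

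**Reproducing the plan's figure.** Protocol 9.4 equates ~14 weeks with 95 days. 186 − 91 = 95, 180 − 85 = 95 and 494 − 399 = 95. It reproduces.

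**Window lengths**

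| Subject | Formula | Days | Ratio |
|---|---|---|---|
| q4wk, continues | 91 − 1 − 6 + 1 | 85 | 1 |
| q4wk completer, does not continue | 186 − 6 + 1 | 181 | 181/85 = 2.13 |
| q4wk, stops at Day 35 | 35 + 95 − 6 + 1 | 125 | 125/85 = 1.47 |
| q4wk completer, with SAP 4.1.4's ~2 weeks | 91 + 14 − 6 + 1 | 100 | 100/85 = 1.18 |
| q2wk, continues | 85 − 1 − 1 + 1 | 84 | 1 |
| q2wk completer, does not continue | 180 − 1 + 1 | 180 | 180/84 = 2.14 |

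Of the completing non-continuer's 181 days, 95 (52%) fall after the Day 91 visit. The same subject's exposure window is 91 − 1 + 1 = 91 days.

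**Effect on the percentage.** At a constant rate r per subject-year, P(at least one event) = 1 − exp(−r × days/365.25). The last column is the difference between the two groups divided by 8.

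| r (assumed) | Continuer, 85 days | Completing non-continuer, 181 days | Shift per non-continuer in an arm of 8 |
|---|---|---|---|
| 0.5 | 11.0% | 21.9% | 1.4 points |
| 1 | 20.8% | 39.1% | 2.3 points |
| 2 | 37.2% | 62.9% | 3.2 points |
| 4 | 60.6% | 86.2% | 3.2 points |

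At r = 1, an arm of 8 has expected incidence 20.8% with no non-continuers, (6 × 20.8 + 2 × 39.1)/8 = 25% with two, and 30% with four.

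**Effect on the rate per SC injection.** At r = 2, a completer has three injections either way: 2 × 85/365.25/3 = 0.16 events per injection for a continuer and 2 × 181/365.25/3 = 0.33 for a non-continuer.

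**Effect on the subject-year rate.** At a constant rate, events and time grow together and nothing changes. If no events at all occurred in follow-up, two non-continuers in an arm of 8 would still raise its person-time by a factor of (6 × 85 + 2 × 181)/(8 × 85) = 1.28 and dilute the rate accordingly.

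**The case against.** The strongest reply is that following events through washout is sound and prespecified. It stands. At a half-life of ~19 days, Day 91 is 28/19 = 1.5 half-lives after the Day 63 dose and Day 186 is 123/19 = 6.5. A reader might infer that follow-up is drug-free and its events irrelevant. The documents do not support that: these subjects are off dosing, but drug is still present at Week 13. The protocol's observation period for events also runs to Day 186 for them. The problem is the Treatment Period 1 label, not the collection.

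A reader might also infer that the plan builds unequal windows between arms. It does not. The window depends on continuation, every subject may enter Treatment Period 2, no non-continuation figures are given, and no test on adverse events is planned. Nor does 2.13 apply to every non-continuer: it is the case of a completer who declines Treatment Period 2.

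A further tempting inference is that inflated counts feed the adverse-drug-reaction rule in SAP 11.7(d). That rule compares exposure-adjusted incidence rates. If these use the same windows, extra events come with extra time, and distortion arises only if the event rate in follow-up differs from that on dosing. The subject-year rate in SAP 11.3 is likewise coherent, because its time runs over the same evaluation period as its events.

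Finally, SAP 8.2.8 introduces its periods as denominators. That does not answer the point, because SAP 11 and 11.3 use them for the safety tables and count events to Follow-up.

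**Conclusion.** The inconsistency is real. Non-continuers' events after Treatment Period 1 enter the Treatment Period 1 subject percentages and per-injection rates, contrary to protocol Table 2 and to the SAP's own exposure and efficacy cut-offs.

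The effect is modest and conditional. It distorts the arm comparison only if non-continuation differs by arm, and vanishes if everyone continues. It amounts to about 2 to 3 percentage points per completing non-continuer in an arm of 8 at an assumed 1 to 4 events per subject-year, and about 1.4 points at 0.5. For comparison, one subject in such an arm is 12.5 points. Early stoppers shift it less, because their windows are shorter.

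These figures assume a constant event rate and the protocol's 95-day follow-up. The ~2-week figure in SAP 4.1.4 would reduce the completer's ratio to 1.18. The windows stay unequal either way, and the two passages must be reconciled.

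**What to change.** In SAP 8.2.8 and 11.3, define one Treatment Period 1 adverse-event window for all subjects: from the first SC dose to the earlier of the first Treatment Period 2 dose or the nominal Week 13 day (Day 91 for q4wk, Day 85 for q2wk). On-schedule completers then contribute 85 days (q4wk) or 84 (q2wk) whether or not they continue, or one day more if the SAP's subtraction of 1 is dropped for everyone.

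For early stoppers, count events to the nominal day rather than closing at their Study Completion Visit. Closing there would give a Day-35 stopper 35 − 6 + 1 = 30 days. At 2 events per subject-year that is a 15% chance of an event against 37% for a continuer. This is further from parity than the present 50% against 37%, and it drops events while drug is still present. The protocol's scheduled follow-up already supplies the data: even a subject who stops at Day 6 is followed to about Day 6 + 95 = Day 101. This relies on the 95 days, so SAP 4.1.4 has to be reconciled with the protocol first.

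Use the common window for the Treatment Period 1 percentages and rates. Tabulate events from its end to Follow-up in a separate post-treatment block with its own person-time. State where events fall if a continuer's first Treatment Period 2 dose comes after the nominal day, so that none is lost.

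The cost is SAP wording and one extra table block, with no new data. The downside is that washout-period events are shown apart from the Treatment Period 1 total.

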**Treatment Period 1 (CCI [REDACTED]):**

Week 13 Day 85 Visit date and time – 1 – Week 1 Day 1 Visit of Treatment Period 1 date and time (the date / time of first SC administration of investigational product in Treatment Period 1) + 1.

**Treatment Period 1 (CCI [REDACTED]):**

Follow-up or Study Completion Visit date and time (whichever occurs later) – Week 1 Day 1 Visit of Treatment Period 1 date and time (the date / time of first SC administration of investigational product in Treatment Period 1) + 1.

**Treatment Period 2 (subjects without dose change):**

Follow-up or Study Completion Visit date and time (whichever occurs later) – Week 13 Day 85/91 Visit date and time + 1.

**Treatment Period 2 (subjects with dose change):**

Portion before dose change:

Date and time of dose change – Week 13 Day 85/91 Visit date and time + 1.

Portion after dose change:

Follow-up or Study Completion Visit date and time (whichever occurs later) – Date and time of dose change.

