3.3 Scientific Rationale

3.3.1 Study Design Rationale

The present phase 2 study will evaluate the efficacy, safety, tolerability, and PK profile of multiple subcutaneous administrations of CSL312 across a range of doses in subjects with C1-INH HAE or FXII/PLG HAE. The study consists of a Screening Period to assess subject eligibility, a Run-in Period to assess underlying disease activity, and 2 treatment periods to assess initial and long-term (respectively) safety, tolerability, and efficacy. The data from this study will be used to select dose(s) for a potential phase 3 study.

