**Treatment Period 1 and 2 (subjects with dose change):**

Portion before dose change:

Date and time of dose change – date and time of first SC administration of study treatment + 1.

Portion after dose change:

Data will not be included in the summary tables.

Date and time of first SC administration of study treatment is Week 1 Day 6 or Week 1 Day 1 for those with [REDACTED] an IV loading dose, respectively.

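### In the Treatment Period 2 and combined safety tables, almost all post-treatment Follow-up falls in the reduced-to dose column, so adverse-event rates per year are not comparable across doses

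*SAP*

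**What the plan says.** Safety tables are by actual dose, and a subject whose dose changes moves column at the change (SAP 8.2.7 and 11). SAP 8.2.8 sets the adverse-event (AE) windows for Treatment Period 2:

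- Dose change, portion before: "Date and time of dose change – Week 13 Day 85/91 Visit date and time + 1".
- Dose change, portion after: "Follow-up or Study Completion Visit date and time (whichever occurs later) – Date and time of dose change".
- No dose change: "Follow-up or Study Completion Visit date and time (whichever occurs later) – Week 13 Day 85/91 Visit date and time + 1".

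In the combined Period 1 and 2 table, a subject with a dose change contributes "Date and time of dose change – date and time of first SC administration of study treatment + 1" and nothing afterwards. A subject without one again runs to Follow-up.

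The same section has a second set of windows, for exposure, which stop sooner: "Study Completion Visit date and time – Week 13 Day 85/91 Visit date and time + 1" without a dose change, and "Study Completion Visit date and time – Date and time of dose change" after one.

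SAP 4.3.2 reduces all C1-INH HAE subjects on one dose at the next scheduled visit after they consent to Amendment 2. SAP 7 puts them in the same column as subjects who started on the reduced-to dose. SAP 11.3 summarises treatment-emergent AEs (TEAEs) up to Follow-up and defines subject SC years as the "sum of the time in years that subjects were exposed to study treatment administered by SC injections during the respective safety evaluation period". It then adds, in brackets, a description based on the length of the safety evaluation period. It refers to 8.2.8 without saying which set of windows applies.

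Protocol 9.4 puts the Period 2 Follow-up about 14 weeks (95 days) after the final visit. SAP 4.1.4 puts it about 2 weeks after.

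**The concern.** Follow-up differs from treatment. Dosing has ended, and routine prophylaxis that protocol 7.3 bars during treatment is allowed again by protocol 7.2. Under the SAP windows this time enters one dose column and is nearly absent from the other, and no on-treatment rate is planned beside it. A difference in yearly AE rates between the doses could then reflect where the windows end and not the dose.

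These columns hold the trial's longer-term safety data by dose, and protocol 3.3.1 says: "The data from this study will be used to select dose(s) for a potential phase 3 study".

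**Working it through.** **1. The plan's own figures.** Follow-up length: 494 − 399 = 95 days. The Period 1 schedules agree: 186 − 91 = 95 and 180 − 85 = 95. Period 2: (399 − 91)/7 = 44.0 weeks, as stated.

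**2. Follow-up share of one subject's Period 2 AE window** (protocol Follow-up, no extension):

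- Reduced subject, higher-dose portion: 0 days of Follow-up.
- Unchanged subject: 494 − 91 + 1 = 404 days; 95/404 = 24%.
- After reduction at Day 147: 494 − 147 = 347 days; 95/347 = 27%.
- After reduction at Day 231: 263 days; 95/263 = 36%.
- After reduction at Day 315: 179 days; 95/179 = 53%.
- Combined table, unchanged subject: 494 − 6 + 1 = 489 days; 95/489 = 19%.

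**3. Whole reduced-to column.** Assumption: all 40 C1-INH HAE subjects continue. Eight stay on each of the two doses and 24 are re-randomized 1:1, which gives 20 starting Period 2 on each. All 20 on the higher dose are reduced on the same day, and there are no dose increases. For Day 231:

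- Total: 20 × 404 + 20 × 263 = 13,340 days.
- Follow-up: 40 × 95 = 3,800 days (28.5%).
- On treatment: 13,340 − 3,800 = 9,540 days.

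**4. Effect on the yearly rate.** Let f be the AE rate in Follow-up relative to the on-treatment rate. The documents do not give f. True on-treatment rates are set equal for the two doses, so an undistorted ratio (reduced-to over reduced-from) is 1.00.

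- AE windows as denominator: (on treatment + f × Follow-up)/total.
- Exposure windows as denominator, TEAEs counted to Follow-up: 1 + f × Follow-up/on treatment.

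| Reduction day | Follow-up share of column | AE windows, f = 0 | AE windows, f = 0.5 | AE windows, f = 1 | Exposure windows, f = 0.5 | Exposure windows, f = 1 |
|---|---|---|---|---|---|---|
| 147 | 25% | 0.75 | 0.87 | 1.00 | 1.17 | 1.34 |
| 231 | 28.5% | 0.72 | 0.86 | 1.00 | 1.20 | 1.40 |
| 315 | 33% | 0.67 | 0.84 | 1.00 | 1.24 | 1.48 |

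f = 0 describes events that need a dose, such as injection site reactions or AEs within 24 hours of an injection. With f = 1.25, the AE-window ratio at Day 231 is 14,290/13,340 = 1.07.

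**5. What shrinks it.**

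- Extension by x days: an unchanged subject's share is 95/(404 + x). It falls below 10% when x exceeds 950 − 404 = 546 days, about 18 months. With Period 2 ending at Day 483 or Day 567, the column share for a Day 231 reduction is 23% or 19%.
- The SAP's Follow-up of about 2 weeks (14 days): for Day 231 the column is 20 × 323 + 20 × 182 = 10,100 days, of which 40 × 14 = 560 (5.5%) is Follow-up. For reductions from Day 119 to Day 315 the share is 4.5% to 6.7%, and the AE-window ratio at f = 0 is 0.96 to 0.93.

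**6. After the change proposed below.** For Day 231 the windows become 141 days on the higher dose and 399 − 231 = 168 days on the reduced-to dose. Neither contains Follow-up, and the ratio is 1.00 for any f.

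**The case against.** **The allocation follows the plan's own rule.** Columns are by actual dose, and someone who has been reduced can have no post-treatment time on the higher dose. Counting TEAEs to Follow-up matches the observation period in protocol 9.4. This stands: the allocation is not an error. What is missing is a split between on-treatment and Follow-up time.

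**Follow-up is not drug-free.** A reader might call it off-drug time. With the half-life of about 19 days in protocol 1.2.3.1, 95 days is five half-lives: the level falls to about 3% of its final-visit value by the end but starts well above that. Follow-up is off dosing, and some of its events occur under residual drug. Likewise, events soon after a reduction occur under residual higher-dose drug.

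**Dilution of the lower dose's rates is not shown in general.** A reader might infer it from the windows. It requires the AE windows as denominator and fewer AEs in Follow-up than on treatment. The AE windows are the likelier reading, because in Period 1 and the combined table they start at the first SC dose while the exposure windows start at the first dose by any route. But SAP 11.3 does not say so, SAP 11.1 ties exposure to the safety evaluation periods too, and f is unknown. Nor are background events counted only on the lower dose: those arising before the reduction are counted on the higher dose.

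**Other summaries exist.** The SAP also plans subject counts, percentages and rates per SC injection. For injection-linked events the per-injection rate is unaffected. For other events Follow-up adds events but no injections, so that rate rises in the reduced-to column.

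**The tables are secondary in rank.** They are open-label and descriptive. The secondary safety endpoint is the number and percentage of subjects with events in Treatment Period 1, and for subjects who continue, the Period 1 AE window has no Follow-up. This limits the importance but does not remove the imbalance.

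**Conclusion.** The point holds as a lack of comparability. The reduced-from column has almost no Follow-up. The exception is anyone who stopped before the reduction, whose Follow-up stays there. A subject whose dose was increased and not later reduced carries Follow-up under the increased dose. The reduced-to column carries about 24% for unchanged subjects and 27% to 53% for subjects reduced at Day 147 to 315.

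The stronger conclusion, that the lower dose will look safer than it is, is not supported. At a Day 231 reduction the column ratio runs from 0.72 (dosing-linked events, AE windows) through 1.00 (f = 1, AE windows) to 1.40 (f = 1, exposure windows). Under neither denominator is the rate protected from the Follow-up imbalance.

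These sizes rest on the protocol's 95-day Follow-up, no extension, and 20 unchanged plus 20 reduced subjects. They are much smaller under the SAP's Follow-up length and fall with extension. The SAP should be changed before the safety tables are produced; the Treatment Period 1 secondary safety endpoint is unaffected for subjects who continue into Period 2.

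**What to change.** - In SAP 8.2.8 and 11.3, report on-treatment AE counts and rates per subject-year by dose, with numerator and denominator both ending at the dose change or the Study Completion Visit, whichever comes first. State that this window is the denominator for subject SC years.
- Tabulate TEAEs from Study Completion to Follow-up separately, by last dose received.
- Apply the same split to Treatment Period 1 subjects who do not continue, whose AE windows also run to Follow-up.
- Reconcile the Follow-up length in SAP 4.1.4 with the protocol.

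Cost: SAP wording and one extra AE table, with no new data. The downside is that Follow-up events, including those under residual drug, no longer appear in the on-treatment columns. They remain tabulated and listed.
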